7. Thompson FE et al. (2004) Performance of a short tool to assess dietary intakes of fruits and vegetables, percentage energy from fat and fibre. Public Health Nutrition, 7(8), 1097-1106.

3.6. Research Design and Methods:

This is a two-arm individually randomized trial. The Counselor-initiated group will follow a more intense counselor-initiated approach, where the counselor schedules weekly telephone sessions and contacts the group participants directly. The Self-paced group uses a less intense approach, where the participants can receive the same telephone counseling sessions as the counselor-initiated group, only if they call the counselor. Neither of the intervention groups are controls, and both treatments are expected to result in weight reduction. A more detailed description of each randomization group is located below in section 3.6.1.

Potential participants will be recruited through the use of advertisements, electronic bulletins, emails, newspapers, and word-of-mouth. Persons interested in learning more about the study will call the study phone number, or can request a call back through the website or in person event. If the participant decides that he/she is interested based on initial information by phone, a civilian research staff member will complete a phone-based pre-screening consultation. Through this pre-screening consultation, the individual will receive a more detailed description of the project if they meet eligibility criteria (see Section 3.6.7). If the person is considering participation, they will be scheduled for a screening visit (in-person) at the Lackland AFB Health and Wellness Center (HAWC) within the next week. The pre-screening consultation will take approximately 15 minutes.

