A total of four research-related in-person visits will be required over the 12-month span of the study. All inperson visits will occur at the HAWC and will be conducted by civilian research staff. Adverse events will be assessed at the baseline visit, follow-up visits, and via self-report during the 12-month intervention period.

Retention methods that may be used for telephone session reminders and follow up data collection visits can include: phone calls, emails, and text reminders of appointments, as well as a letter sent via encrypted email to participants from [name] and/or [name]. In addition, we will mail greeting cards to increase retention throughout the year long program. There will also be quarterly e-newsletters and retention events for all active ppts. The newsletter could include such things as tips about weight loss, inform ppts about the next retention event, a featured 5K in the community, recruitment and study updates. Ppts will be given an option to opt out of the e-newsletter. All active ppts will be invited to events related to diet and exercise. Possible events could include guest speakers, classes on healthy food preparation, gardening demonstration, guided tours at a local farmer's market or grocery store.

3.6.1. Interventions, Observations, or Data Sought:

The study will compare two modalities of implementing the successful Look AHEAD intervention. One treatment group will follow a Counselor-initiated approach, while the other group will follow a Self-paced approach.

Procedures for the Counselor-initiated intervention group:

- Individual Telephone Sessions are a main component of this study. Participants will receive 28 telephone sessions over a 12 month period by interventionists trained in behavior change skills (e.g., goal setting, problem solving, relapse prevention, stimulus control) and motivational interviewing techniques. The telephone calls will be designed to provide strategies to help participants with weight loss. Participants will receive a call once a week for the first sixteen weeks (16 calls), every other week for the next 16 weeks (8 calls), and monthly for the duration of the treatment (4 calls). Quality control will be assessed randomly by a study investigator to ensure consistency and fidelity of the intervention. Random quality control is conducted only with the participant's consent.
- Email Communication: Email will be used to provide participants with feedback and suggestions to help with weight loss.

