- Self-Monitoring: Because self-monitoring has been shown to be significantly associated with weight loss, participants will be asked to monitor food intake, physical activity and weight daily. Participants will be asked to use the Lose It app/website which, with their permission, the study staff will be able to access in order to retrieve their food and physical activity information. Monitoring of weight will be facilitated by the use of the BodyTrace e-scale. Each participant will be provided a scale which will upload their daily weight to a secure website (HIPPA compliant) which our study staff can access. Participants will receive feedback on self-monitoring through email.
- Dietary goals: Dietary goals will be based on weight and will be personalized based on participants' weight-loss progress and goals.
- Meal Replacements: Meal replacements will be provided to participants in the counselor-initiated group at no cost. Vouchers for meal replacement products will be given to participants to use at local grocery stores. Participants will be encouraged to replace 2 meals (typically breakfast and lunch) and a snack with meal replacements. Participants may elect not to use meal replacements. If so, detailed meal plans (for all meals) using common foods that are designed to control portion size and calories will be provided to the participant.
- Physical Activity Goals: Taking into account the amount of physical activity for each participant at the beginning of the program, participants will be asked to gradually increase their cardiorespiratory (aerobic) exercise > 5 days per week at a moderate to vigorous intensity level for 40 to 60 minutes per day (each bout lasting a minimum of 10 minutes), until they reach a total of 225-250 minutes per week. Upon reaching the physical activity goal of 225-250 minutes per week, they will be asked to maintain this level of physical activity.
- Toolbox: The Toolbox includes additional treatment options for those who wish to take advantage of them. Items may include: food scales, exercise videos, cookbooks, etc. These items may be checked out from Fit Blue staff members, but must be returned prior to the completion of the study.

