- Challenge There will be several challenges (e.g. 10,000 steps per day for 30 days, dietary selfmonitoring everyday for 30 days) designed to increase participant interest and provide a specific goal (e.g. increase self-monitoring, increase activity level) during the twelve month study period. Participants who successfully complete the challenges will be given a small award (e.g. T-shirt valued at approximately \$4.34). Value of all study-related awards and incentives will not exceed \$50 annual limit/person and do not require any special approval through the Hospital Commander.

Procedures for the Self-paced intervention group:

• Individual Telephone Sessions are provided only when the participant calls the study phone line and requests a session with a counselor. Participants may receive up to 28 telephone sessions over a twelve month period by interventionists trained in behavior change skills (e.g., goal setting,

problem solving, relapse prevention, stimulus control) and motivational interviewing techniques. The telephone calls will be designed to provide strategies to help participants with weight loss. Quality control will be assessed randomly by a study investigator to ensure consistency and fidelity of the intervention. Random quality control is conducted only with the participant's consent.

- Self-Monitoring: Participants will be asked to monitor food intake, physical activity and weight daily. Participants will be asked to use the Lose It app/website which, with their permission, the study staff will be able to access in order to retrieve their food and physical activity information. Monitoring of weight will be facilitated by the use of the BodyTrace e-scale. Each participant will be provided a scale which will upload their daily weight to a secure website (HIPPA compliant) which our study staff can access. Participants will receive feedback, by request only, on selfmonitoring through e-mail.
- Dietary goals: Dietary goals will be based on weight and will be personalized based on participants' weight-loss progress and goals.
- Meal Replacements will not be provided to self-paced participants for the study. However, participants will be encouraged to purchase their own meal replacements, although it is not required. Detailed meal plans (for all meals) using common foods that are designed to control portion size and calories will be provided to the participant.

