After randomization, participants will be upgraded to the Lose It! Premium app and added to the Fit Blue Premium account which will allow study counselors to access their dietary and physical activity logs in order to provide feedback and suggestions. It will also allow this information to be downloaded to the Fit Blue database for further analysis and tracking. In order to upgrade to the Lose It! Premium Fit Blue account, a valid email address different from that used during the screening run-in diary phase will be required. As before, if the participant does not have a second email, or does not wish to use a current personal email address to access the Lose It! Premium Fit Blue account, study staff will assist them in creating a new email account to use that will provide them with the necessary access for participation. Lose It provides their Premium version to the University of Tennessee Health Science Center as a gift at no cost.

- Provide study materials based on group assignment, including FIT Blue participant lesson materials (for the counselor-initiated group only), Body Trace electronic scales, measuring cups and spoons, and exercise guidelines.
- Self-paced group will be given instructions on how to receive counseling from study staff if desired and a T-shirt (Counselor-initiated group given T-shirt at time of Self-Monitoring Challenge)
- Assess for adverse events
- The counselor-initiated group will be given an appointment for their first counseling session.

Follow-up visit (in-person at 4 months):

- Height, weight, abdominal circumference, resting blood pressure and resting heart rate will be measured
- Complete the dietary, physical activity, and weight-related attitudes and behavior questionnaires
- Quality of Life questionnaire (re-administered by study personnel)
- Assess for adverse events

Follow-up visit (in-person at 12 months):

- Height, weight, abdominal circumference, resting blood pressure and resting heart rate will be measured
- Complete the dietary, physical activity, and weight-related attitudes and behavior questionnaires
- Quality of Life questionnaire (re-administered by study personnel)
- Assess for adverse events
- Program evaluation
- Air Force Fitness Test scores will be collected (only for Air Force personnel) through Health Promotion personnel

Additional procedures for participants who are going to deploy/PCS/separate/retire or have an extended TDY:

- DEPLOYED: Protocol for 4 month and 12 month data collection

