The study aims to enroll 248 participants, 124 participants in each group. This distribution will provide a diverse representation within each intervention group and will provide the necessary information for data and power analysis.

6.3. Statistical Analysis:

The primary data analysis will adhere to the intention-to-treat principle and in the final analysis, the participants will be categorized according to their initial randomization. We will be using the baseline weight as a covariate in the final primary model where we compare the two arms in terms of the percentage of weight loss. We also plan to carry out secondary analyses where we will investigate the efficacy of the intervention in subgroups of Airmen based on gender, race, and years of service in the Armed Forces. We will also evaluate the impact of adherence on outcome, whether it is number of intervention sessions completed, or adherence to dietary intake and physical activity recommendations. Finally, we'll determine the prevalence of Adverse Events and Serious Adverse Events in the two treatment conditions.

6.4 Number of Subjects:

Number of subjects planned for WHASC	Enrolled in full study	248	to result in	248	completing the full study.
TOTAL NUMBER OF SUBJECTS (nation-wide/study-wide):248					

7. Duration of Study: Approximate duration of the study: 54 months

8. Local and External Support Services:

A letter of support from the 559th Medical Group Commander (559 MDG/CC) is attached. The Health and Wellness Center on Lackland AFB will also provide work space for three study staff members as well as for participant visits/follow ups.

9. Intramural (GME) and Extramural Funding Support:

The National Institute of Diabetes and Digestive and Kidney Diseases provided extramural funding for this study.

10. Conflict of Interest:

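### Is the section 6.3 adherence analysis unsound because the session count means scheduled attendance in one arm and optional use of counseling in the other?

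*Combined protocol and SAP*

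**What the plan says.** Section 6.3 (Statistical Analysis) sets out the primary comparison of percentage weight loss by randomized arm, with baseline weight as covariate. It then adds subgroup analyses and an intention to "evaluate the impact of adherence on outcome, whether it is number of intervention sessions completed", with adherence to the diet and activity advice named as the alternative measure. That clause is all the plan says on adherence analysis. It gives no model and no definition by arm, and it does not say whether the arms are pooled or taken separately.

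The two arms reach a session by different routes. In section 3.6.1 the counselor-initiated arm has a fixed schedule: 16 weekly calls, 8 every other week and 4 monthly. In the self-paced arm, sessions are "provided only when the participant calls the study phone line and requests a session with a counselor", and "Participants may receive up to 28 telephone sessions over a twelve month period". Section 3.6 describes the self-paced approach as one "where the participants can receive the same telephone counseling sessions as the counselor-initiated group, only if they call the counselor". Section 3.6.2 (baseline visit) adds: "Self-paced group will be given instructions on how to receive counseling from study staff if desired".

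**The concern.** In the counselor-initiated arm, completed calls can be read against 28 scheduled calls, so the count is a fair measure of adherence. In the self-paced arm, 28 is a ceiling and the visible text sets no expected number. Someone in that arm who never calls has still followed the assigned program, yet would score zero on a measure labelled adherence. The same variable would then record attendance in one arm and help-seeking in the other.

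An analyst might put both arms into one regression of weight loss on sessions and add an arm term. That term absorbs other differences between the arms, such as the free supply described in section 3.6.1 ("Meal replacements will be provided to participants in the counselor-initiated group at no cost"). It still leaves one slope for two behaviours. A reported effect of session adherence could then mainly describe which self-paced participants chose to ask for calls.

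**Working it through.** **The plan's own figure.** Scheduled counselor-initiated calls: 16 + 8 + 4 = 28, which matches the stated total. It is the only session figure in the plan that the point depends on.

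**What a common slope would estimate.** In least squares with an arm term and a single session slope, the fitted slope is

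b = (1 − w)·b_C + w·b_S, with w = s_S² / (s_C² + s_S²) for equal arm sizes,

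where C is counselor-initiated, S is self-paced, b_C and b_S are the within-arm slopes, and s_C and s_S are the within-arm standard deviations of the session count. As a check on the formula, take assumed slopes of 0.25 and 0.50 and SDs of 8 and 4. Then w = 16/80 = 0.20 and b = 0.8 × 0.25 + 0.2 × 0.50 = 0.300. A simulation with 200,000 per arm gave 0.300, and adding an arm-by-sessions interaction returned 0.249 and 0.502. So the blending is real if one slope is fitted, and the interaction removes it.

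**Inputs for a sense of size.** Only the 124 per arm comes from the plan (section 6.2). Assumed: outcome SD 6 percentage points; counselor-initiated sessions with mean 21 and SD 5.2; self-paced sessions with mean 1, 3 or 8 and SD 1.4, 3.5 or 7.4.

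**Weight of the self-paced arm.**
- Mean 1: 1.96 / (27.04 + 1.96) = 0.07
- Mean 3: 12.25 / (27.04 + 12.25) = 0.31 (30% in simulation)
- Mean 8: 54.76 / (27.04 + 54.76) = 0.67

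**Case A: attendance unrelated to loss, self-paced slope 0.2 points per call.** The common slope is 0.2w, with SE = 6 / √[124 × (s_C² + s_S²)].
- Mean 1: 0.014 / 0.100, giving z = 0.14 and significance in about 5% of trials
- Mean 3: 0.062 / 0.086, giving z = 0.73 and about 11%
- Mean 8: 0.134 / 0.060, giving z = 2.2 and about 61%

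Simulation gave 5–6%, 11% and 59–60%. With 99 per arm and SD 7 it gave 5–6%, 8–9% and 38–40%.

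The last figure in each set is not a false-positive rate, because a true association exists in the self-paced arm. That arm alone has SE = 6 / (7.4 × √124) = 0.073 and z = 0.2 / 0.073 = 2.7, so it would show the association in about 78% of trials (about 76% in simulation).

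**Case B: opposite slopes, +0.2 counselor-initiated and −0.2 self-paced.** Here b = 0.2 × (1 − 2w), which gives +0.17, +0.08 and −0.07. The sign depends on how often self-paced participants call.

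**Case C: equal slopes.** Then b equals the shared slope whatever the SDs, and nothing is distorted.

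**What the plan commits to.** Set beside these cases, section 6.3 specifies none of the fitted models. A by-arm analysis and an interaction model are both consistent with its wording, and neither blends the slopes.

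**The case for a change.** The strongest case for acting is that the difference in meaning is built into the design. The trial compares counselor-initiated with participant-initiated calls, so session count cannot be the same kind of adherence in both arms. An arm term, which many analysts would add by habit, does not repair this. A sentence of clarification would cost almost nothing and would guard against a misleading published result.

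The description stands: section 6.3 does not define session adherence by arm, and a common slope would be a blend. What does not stand is that the plan makes this error, since the common slope has to be supplied by the reader. The two-measures argument is also partly a matter of label. Section 3.6 offers the self-paced arm the same sessions, so as a count of counseling received the variable means the same thing in both arms. What differs is how sessions arise. Selection by motivation affects attendance at scheduled calls as well, so it is not peculiar to the self-paced arm. The absence of a target can be asserted only for the visible text, because section 13 lists self-paced lesson materials that are not reproduced.

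A stricter definition is not a clear gain either. Counting only the first 16 weekly calls, to limit calls that respond to earlier weight change, would drop 12 of the 28 scheduled calls. Under the assumptions above, the standard error in the counselor-initiated arm rises from 0.10 to 0.17 points per call. The slope detectable at 80% power rises from 0.29 to 0.48. Motivation would remain as a confounder.

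**Conclusion.** The concern does not call for a change. The plan leaves the model for one secondary analysis unstated. The obvious ways to carry it out, by arm or with an arm-by-sessions interaction, avoid the problem. Because who initiates the calls is the trial's central contrast, an analyst would be expected to see that session counts are not interchangeable between arms and to read the results as associations.

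The possible size of the blend ranges from nothing (rare self-paced calls, or equal slopes) to a change of sign (a self-paced mean of 8 calls with opposite slopes). Every session count, SD and slope behind that range is assumed; the documents supply none of them. The primary intention-to-treat comparison of percentage weight loss does not use session counts and is unaffected.

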14.4. Joint Study. N/A
